6.1 Screening Assessments

Must be performed from day -28 to day 1, prior to the scheduled mastectomy and tissue-expander placement:

- Medical history
- Physical examination (including height and weight)
- Vital signs (blood pressure, pulse rate, respiratory rate, temperature)
- Con-Med review
- CBC with differential
- Serum biochemical panel including creatinine, fasting glucose, potassium, sodium, chloride, bicarbonate, ALT/AST, total bilirubin
- Blood or urine pregnancy test

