6.2 Assessments and procedures during treatment

Once the patient is confirmed to be eligible based on screening assessments, the following study assessments will be performed. See Table 6 for summary. Cohort A participants will begin treatment with zafirlukast on post-operative day one (+/- 5 days) following placement of tissue expander(s) after the participant is determined safe from a surgical recovery standpoint. Cohort A participants will take zafirlukast twice per day until the patient has completed expansion of the tissue expander. Zafirlukast should be stopped prior to expander implant exchange. Patients will be randomized on the day of surgery by a study personnel other than the surgeon. The surgeon and patient will be informed of the assigned cohort immediately post-surgery.

Research Visits (+/- 1 week)

- Physical examination (including height and weight)
- Vital signs (blood pressure, pulse rate, respiratory rate, temperature)
- Con-Med and AE review
- CBC with differential and platelet count
- Serum biochemical panel including creatinine, fasting glucose, potassium, sodium, chloride, bicarbonate
- Liver function tests: alkaline phosphatase, ALT/AST, total bilirubin (only for Cohort A)

Expander-Implant Exchange

- Tissue specimen collection

End of Treatment (14 days (+/- 3 days) of expander-implant exchange)

- Medical history, physical examination (including height and weight), vital signs (blood pressure, pulse rate, respiratory rate, temperature)
- CBC with differential and platelet count
- Serum biochemical panel including creatinine, fasting glucose, potassium, sodium, chloride, bicarbonate
- Liver function tests: alkaline phosphatase, ALT/AST, total bilirubin (only for Cohort A)
- Con-Med and AE review

Follow up

Patients are followed for two years after implant reconstruction. After implant exchange we will see patients every 2 weeks for the first month, every month for the subsequent 4 months, and, every 6 months for the remainder of the two years. For those patients removed from the treatment, they will be followed as per our standard of care which is monthly for the first six months and then every six months for a total of two years.

- Physical examination (including height and weight), vital signs (blood pressure, pulse rate, respiratory rate, temperature)

Table 6. Schedule of Study Procedures and Assessments

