Period/ Procedure	Screening ⁹	Treatment period (+/- 1 week)				Expander- implant exchange	End of Treatment	Follow up visits ⁵
Study Day/Visit Day	Days -28 to Day 1	Mastectomy and Tissue- expander placement (week 0)	Day 15-21 (wk 2)	Day 29-35 (wk 5)	Day 71-77 (wk 11)	Day 113-119 (wk 17) ⁸		
Informed Consent	x							
Baseline Conditions ¹	x							
Tissue Specimen Collection						x		
Zafirlukast ⁶		x						
Medical History	x						x	
Vital Signs	x		x	x	x	x	x	x
Physical Exam	x		x	x	x	x	x	x
Con-med and AE review ⁷		x					x	
CBC w/diff ²	x		x	x	x	x	x	
Chemistry ³	x		x	x	x	x	x	
Liver Function Tests ⁴	x			x			x	
Pregnancy Test (HCG)	x							

1. Baseline conditions assessment per DSMC policy.
2. Including CBC with differential and platelet count.
3. Including creatinine, fasting glucose, potassium, sodium, chloride, bicarbonate.
4. Including alkaline phosphatase, ALT/AST, total bilirubin. For Cohort A only on week 5 and EOT. Alkaline phosphatase is not required for screening.
5. Patients are followed for two years after implant reconstruction. After implant exchange we will see patients every 2 weeks for the first month, every month for the subsequent 4 months, and, every 6 months for the remainder of the two years. For those patients are removed from treatment, they will be followed as per our standard of care which is monthly for the first six months and then every six months for a total of two years.
6. 20mg PO twice per day from Day 1 to Treatment Termination for Cohort A only. Treatment may continue until tissue expansion is complete. Zafirlukast should be stopped prior to expander implant exchange.
7. Con-med and AE review begins 28 days prior to treatment and continues 30 days after treatment termination.
8. As needed .
9. Screening procedures must be completed prior to mastectomy and tissue-expander placement.

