8.2 Definition of Adverse Event

An adverse event (also known as an adverse experience) is defined as any untoward medical occurrence associated with the use of a drug in humans, whether or not considered drug related. More specifically, an adverse event can be any unfavorable and unintended sign (e.g., an abnormal laboratory finding), symptom, or disease temporally associated with the use of a drug, without any judgment about causality. An adverse event can arise from any use of the drug (e.g., off-label use, use in combination with another drug) and from any route of administration, formulation, or dose, including an overdose.

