8.4 Evaluation of an Adverse Event

All grade 3 and above adverse events will be entered into OnCore®, whether or not the event is believed to be associated with use of the study drug.

The Investigator will assign attribution of the possible association of the event with use of the investigational drug, and this information will be entered into OnCore® using the classification system listed below:

Relationship	Attribution	Description
Unrelated to investigational drug/intervention	Unrelated	The AE is clearly NOT related to the intervention
	Unlikely	The AE is doubtfully related to the intervention
Related to investigational drug/intervention	Possible	The AE may be related to the intervention
	Probable	The AE is likely related to the intervention
	Definite	The AE is clearly related to the intervention

Signs or symptoms reported as adverse events will be graded and recorded by the Investigator according to the CTCAE. When specific adverse events are not listed in the CTCAE they will be graded by the Investigator as none, mild, moderate or severe according to the following grades and definitions:

- Grade 0 No AE (or within normal limits)
- Grade 1 Mild; asymptomatic or mild symptoms; clinical or diagnostic observations only; intervention not indicated
- Grade 2 Moderate; minimal, local, or noninvasive intervention (e.g., packing, cautery) indicated; limiting age-appropriate instrumental activities of daily living (ADL)
- Grade 3: Severe or medically significant but not immediately life-threatening; hospitalization or prolongation of hospitalization indicated; disabling; limiting self-care ADL
- Grade 4: Life-threatening consequences; urgent intervention indicated
- Grade 5: Death related to AE

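### Alkaline phosphatase is scheduled in Cohort A after zafirlukast starts but waived at screening, so an elevation could be misread as treatment-emergent

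*Combined protocol and SAP*

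**What the plan says.** Screening (section 6.1) requires this chemistry: "Serum biochemical panel including creatinine, fasting glucose, potassium, sodium, chloride, bicarbonate, ALT/AST, total bilirubin". Alkaline phosphatase is not in the list. Table 6 marks liver function tests at screening, but footnote 4 removes this one component: "Alkaline phosphatase is not required for screening".

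After screening, section 6.2 gives the panel, under both the research visits and the end-of-treatment visit, as "Liver function tests: alkaline phosphatase, ALT/AST, total bilirubin (only for Cohort A"). Footnote 4 fixes the timing: "For Cohort A only on week 5 and EOT". Cohort A is the zafirlukast arm; footnote 6 of the same table gives the drug as "20mg PO twice per day from Day 1 to Treatment Termination for Cohort A only".

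On events, section 8.2 allows an adverse event to be "any unfavorable and unintended sign (e.g., an abnormal laboratory finding), symptom, or disease temporally associated with the use of a drug". Section 8.1 directs the assessment at events that are new or worsening.

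**The concern.** Whether a laboratory value is new or worsening can be judged only against an earlier value. ALT, AST and bilirubin have one by requirement; alkaline phosphatase does not. If a Cohort A patient has a raised result at week 5 or at end of treatment, the required data cannot show whether she had it before surgery, whether it has risen, or whether it is new. A pre-existing elevation could be taken for a drug effect.

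The organ system makes this worth raising. Hepatic dysfunction is the side effect that section 4.1 singles out for a patient warning. The section calls it rare but mentions liver failure leading to transplantation and death. The trial is also open-label (section 6.3), so whoever attributes the finding knows that the patient is on the drug. At stake is the reading of individual liver results in treated women, not the efficacy conclusion.

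**Working it through.** The plan states no figure on this point, so there is nothing to reproduce. The check sets the schedule beside the event rules.

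**Step 1: what is required, and when** (sections 6.1 and 6.2; Table 6 with footnote 4)

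| Test | Screening, both cohorts | Week 5 and end of treatment, Cohort A | After screening, Cohort B |
|---|---|---|---|
| ALT/AST | required | required | not scheduled |
| Total bilirubin | required | required | not scheduled |
| Alkaline phosphatase | waived | required | not scheduled |

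Only the last row has a value after the drug starts and none before it. Section 6.1 and footnote 4 agree with each other, so this is a stated choice and not a conflict. The documents give no reason for it.

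**Step 2: could a pre-existing elevation be caught another way?** Eligibility (section 3.3.1, criterion 6; section 3.3.2, criterion 5) uses AST/ALT and bilirubin and sets no limit on alkaline phosphatase, so a raised value is not screened out. Table 6 includes a baseline conditions assessment under a DSMC policy whose content is not given. Medical history is taken, but a silent elevation that nobody has measured would not appear in it.

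**Step 3: what happens to an abnormal value?** It can be an adverse event under section 8.2, and the investigator assigns attribution under section 8.4. Whether a mild elevation reaches the database is unclear. Section 8.4 says "All grade 3 and above adverse events will be entered into OnCore", as does Appendix 1 section 3.1, while section 8.6 has adverse events of every grade entered.

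**Step 4: does follow-up break down?** Section 6.4 follows treatment-related events, in patients removed because of them, down to Grade 1 or back to baseline. Without a baseline the second limb cannot be applied, but the first still can. Section 8.5 gives a further end point, 30 days or resolution or stabilization.

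**Step 5: scale.** The number affected cannot be derived, because the documents give no prevalence p of raised alkaline phosphatase before surgery. For illustration only, with p assumed and n = 45 in Cohort A (section 6.3):

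- Expected number with a pre-existing elevation = 45 × p.
- Chance of at least one = 1 − (1 − p)^45.

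| Assumed p | 45 × p | Chance of at least one |
|---|---|---|
| 1% | 0.45 | 36% |
| 2% | 0.9 | 60% |
| 5% | 2.25 | 90% |
| 10% | 4.5 | 99% |

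These count patients with a pre-existing elevation. To be misread, the value must also still be raised at a scheduled test, be recorded, and be judged new. The documents give no rate for any of these steps.

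**The case against.** The strongest reply is that this was a deliberate and harmless economy. The protocol defines hepatic impairment by AST and ALT and puts bilirubin among the organ-function criteria, and all three have a screening value. A waiver does not forbid the test, and earlier clinical results may exist. The investigator can judge a finding unlikely to be related or unrelated. No efficacy endpoint or planned test uses alkaline phosphatase, and section 9 specifies no comparison of adverse events between arms.

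Most of this stands, and it keeps the point small. It does not remove it. Incidental earlier results would be available for some patients and not others, and attribution is the very judgement that a baseline would inform.

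A reader might infer more than the documents support:

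- **That pre-existing elevations will be counted as new events.** No rule says so. The assessment is for new or worsening events, and attribution is left to judgement. They could be misread; that is as far as the text goes.
- **That roughly 1 to 5 Cohort A patients would be falsely classed.** That range is 45 × 2% to 45 × 10%, rounded. It rests on an assumed prevalence and takes every pre-existing elevation as persistent, recorded and judged new.
- **That the follow-up rule is undefined for this marker.** Only its baseline limb is lost; the Grade 1 limb remains.
- **That patients would be taken off treatment needlessly.** No discontinuation criterion in the protocol is tied to alkaline phosphatase.
- **That the waiver is what confines such findings to the zafirlukast arm.** The cause is that every liver test after screening is restricted to Cohort A. The same asymmetry affects ALT/AST and bilirubin.

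**Conclusion.** The point holds in a limited form. Alkaline phosphatase is the only scheduled liver test with no protocol-required pre-drug value, so an elevation in a Cohort A patient could be misread as treatment-emergent. The conclusion rests on the schedule alone and needs no assumption about prevalence. How many patients would be affected is unknown, and the figures above are illustrative.

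The primary and secondary analyses are untouched. This is a worthwhile but minor improvement to the interpretation of safety data.

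**What to change.** 1. Add alkaline phosphatase to the screening chemistry in section 6.1. Randomization takes place on the day of surgery, so the arm is not known at screening and the test would apply to all patients.
2. Delete the last sentence of Table 6 footnote 4.
3. State in section 9.1 that the Cohort A week 5 and end-of-treatment values will be summarised descriptively as change from the screening value.

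The cost is one extra analyte on a sample already drawn. No visit, procedure or clinical rule changes.

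The gain is a within-patient baseline for treated women, so that new or worsening can be judged for this marker. It will not show whether a change is due to the drug, and it will not make liver safety comparable between arms, since Cohort B would still have no scheduled liver tests after screening.

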6.3 Randomization Procedures

This study is an open-label randomized trial; therefore the investigator and subject will know the treatment administered. Patients will be randomized by a study personnel other than the surgeon. The surgeon and patient will be notified of the patient's cohort immediately post-surgery. Two arms will be tested, with each independent assessment. Patients will be block randomized to either treatment with zafirlukast or the standard of care. Enrollment will continue until 90 patients (45 per cohort) have been enrolled.

6.4 Duration of Therapy

In the absence of treatment delays due to adverse events, treatment may continue until tissue expansion is complete or until:

- Illness that prevents further administration of treatment
- Unacceptable adverse event(s)
- Patients decides to withdraw from the study
- Significant patient non-compliance with protocol
- General or specific changes in the patients' condition render the patient unacceptable for further treatment in the judgment of the investigator.

Patients are routinely followed for two years after undergoing implant based reconstruction. In this study we will initially see patients periodically for research visits until tissue expansion has been completed. After implant exchange we will see patients every 2 weeks for the first month, and every month for the subsequent 4 months. We will then see them every 6 months for the remainder of the two years. Those patients who are removed from treatment will be followed as per our standard of care, which is monthly for the first six months and then every six months for two years. Serious adverse events will be collected for 30 days after the end of treatment, or until death, whichever occurs first. Patients removed from treatment for unacceptable treatment related adverse event(s) will be followed until resolution or stabilization of all treatment related adverse events to Grade 1 or baseline.

Subjects may withdraw consent at any time for any reason, or be dropped from the trial at the discretion of the investigator should any untoward effect occur. In addition, a subject may be withdrawn by the investigator if enrollment into the trial is inappropriate, the trial plan is violated, or for administrative and/or other safety reasons.

6.5 Long Term/Survival Follow-up Procedures

Safety Follow-Up Visit

The mandatory Safety Follow-Up Visit should be conducted approximately 30 days after the last dose of trial treatment. All AEs that occur prior to the Safety Follow-Up Visit should be recorded. Subjects with an AE of Grade > 2 will be followed until the resolution of the AE to Grade 1 or baseline.

6.6 Survival Follow-up

6.6.1 Discontinuation of Therapy

The Investigator will withdraw a patient whenever continued participation is no longer in the patient's best interests. Reasons for withdrawing a patient include, but are not limited to, disease progression, the occurrence of an adverse event or a concurrent illness, a patient's request to end participation, or simply significant uncertainty on the part of the Investigator that continued participation is prudent. There may also be administrative reasons to terminate participation, such as concern about a patient's compliance with the prescribed treatment regimen.

When a subject discontinues/withdraws prior to trial completion, all applicable activities scheduled for the final trial visit should be performed at the time of discontinuation. Any adverse events which are present at the time of discontinuation/withdrawal should be followed in accordance with the safety requirements outlined in Section 8.

6.7 Usage of Concurrent/Concomitant Medications

All treatments that the investigator considers necessary for a subject's welfare may be administered at the discretion of the investigator in keeping with the community standards of medical care. All concomitant medication will be recorded on the case report form (CRF) including all prescription, over-the-counter (OTC), herbal supplements, and IV medications and fluids. If changes occur during the trial period, documentation of drug dosage, frequency, route, and date may also be included on the CRF.

All concomitant medications received within 28 days before the first dose of trial treatment and 30 days after the last dose of trial treatment should be recorded. Concomitant medications administered after 30 days after the last dose of trial treatment should be recorded for SAEs and Events of Clinical Interest (ECI) as defined in Section 8.

6.8 Dietary Restrictions

There are no dietary restrictions within this trial.

6.9 Prohibited Concomitant Medications

Subjects are prohibited from receiving the following therapies during the Screening and Treatment Phase of this trial:

- Anti-cancer systemic chemotherapy or biological therapy

Subjects who, in the assessment by the investigator, require the use of any of the aforementioned treatments for clinical management should be removed from the trial. Subjects may receive other medications that the investigator deems to be medically necessary.

Potential Drug Interactions:

The following drug interaction studies have been conducted with zafirlukast

- Co-administration of multiple doses of zafirlukast (160 mg/day) to steady-state with a single 25 mg dose of warfarin (a substrate of CYP2C9) resulted in a significant increase in the mean AUC (+63%) and half-life (+36%) of S-warfarin. The mean prothrombin time increased by approximately 35%. The pharmacokinetics of zafirlukast were unaffected by co-administration with warfarin.

- Co-administration of zafirlukast (80 mg/day) at steady-state with a single dose of a liquid theophylline preparation (6 mg/kg) in 13 asthmatic patients, 18 to 44 years of age, resulted in decreased mean plasma concentrations of zafirlukast by approximately 30%, but no effect on plasma theophylline concentrations was observed.
- Co-administration of zafirlukast (20 mg/day) or placebo at steady-state with a single dose of sustained release theophylline preparation (16 mg/kg) in 16 healthy boys and girls (6 through 11 years of age) resulted in no significant differences in the pharmacokinetic parameters of theophylline.
- Co-administration of zafirlukast dosed at 40 mg twice daily in a single-blind, parallel-group, 3-week study in 39 healthy female subjects taking oral contraceptives, resulted in no significant effect on ethinyl estradiol plasma concentrations or contraceptive efficacy.
- Co-administration of zafirlukast (40 mg/day) with aspirin (650 mg four times daily) resulted in mean increased plasma concentrations of zafirlukast by approximately 45%.
- Co-administration of a single dose of zafirlukast (40 mg) with erythromycin (500 mg three times daily for 5 days) to steady-state in 11 asthmatic patients resulted in decreased mean plasma concentrations of zafirlukast by approximately 40% due to a decrease in zafirlukast bioavailability.
- Co-administration of zafirlukast with fluconazole, a moderate CYP2C9 inhibitor, resulted in increased plasma levels of zafirlukast, by approximately 58% (90% CI:28, 95). The clinical significance of this interaction is unknown. Zafirlukast exposure is likely to be increased by other moderate and strong CYP2C9 inhibitors. Co-administration of zafirlukast with itraconazole, a strong CYP3A4 inhibitor, caused no change in plasma levels of zafirlukast.

6.10 Contraception

Zafirlukast may have adverse effects on a fetus in utero. Furthermore, it is not known if zafirlukast has transient adverse effects on the composition of sperm. Non-pregnant, non-breast-feeding women may be enrolled if they are willing to use 2 methods of birth control or are considered highly unlikely to conceive. Highly unlikely to conceive is defined as 1) surgically sterilized, or 2) postmenopausal (a woman who is ≥ 45 years of age and has not had menses for greater than 1 year will be considered postmenopausal), or 3) not heterosexually active for the duration of the study. The two birth control methods can be either two barrier methods or a barrier method plus a hormonal method to prevent pregnancy. Subjects should start using birth control from study Visit 1 throughout the study period up to 120 days after the last dose of study therapy.

The following are considered adequate barrier methods of contraception: diaphragm, condom (by the partner), intrauterine device, sponge, or spermicide. Appropriate hormonal contraceptives will include any registered and marketed contraceptive agent that contains an estrogen and/or a progestational agent (including oral, subcutaneous, intrauterine, or intramuscular agents).

Subjects should be informed that taking the study medication may involve unknown risks to the fetus (unborn baby) if pregnancy were to occur during the study.

